5. DETERMINATION OF SAMPLE SIZE

Sample size estimation is based primarily on supine SVC results from the study 3119001 LEVALS (Table 1). LEVALS had placebo-controlled data only up to 2 weeks, and therefore extrapolation of the results was needed. The placebo effect from phase II tirasemtiv trial BENEFIT-ALS (Shefner JM et al., 2016) was also evaluated.

Assuming a difference of at least 3.6% in change from baseline supine SVC between treatment groups and a common standard deviation of 10%, 164 evaluable subjects per group in a 1:1 allocation ratio have 90% power to detect a statistically significant difference in a two-sided, 5% α -level, two group T-test. Using a 2:1 allocation ratio, randomisation of 450 subjects to the study (approximately 300 levosimendan and 150 placebo treated subjects) allows for a total dropout rate of approximately 20%.

Table 1. Mean (SD) change from baseline SVC (supine) %-predicted in LEVALS

Treatment	2 weeks	12 weeks
Levosimendan 1 mg x 2	+2.4 (8.3)	-4.9
Levosimendan 1 mg x 1	+0.8 (8.6)	
Placebo	-3.6 (9.4)	-17.7 ¹
Placebo (BENEFIT-ALS)	-1.4	-8.5

¹ Extrapolated from the data

SD = standard deviation

Based on the dexpramipexole phase III study EMPOWER (Cudkowicz ME et al., 2013), a 12 point reduction in total ALSFRS-R score and a 15% mortality rate at 12 months can be assumed

in placebo treated patients. Assuming a 10 point decline in ALSFRS-R, with a standard deviation of 8 points, and a 20% relative improvement in survival, 450 patients provide approximately 80% simulated power to detect a statistically significant difference using a joint rank test. With 450 subjects and assuming a 48-week levosimendan event rate of 73% and hazard ratio of 0.70, time to respiratory event has approximately 70% power to detect a statistically significant difference using a log-rank test.

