7.5.2.3 Respiratory event and other time-to-event endpoints

A 'time to respiratory event' composite endpoint consists of the following events:

- A decrease of one or more points from baseline in any of the ALSFRS-R respiratory function subdomain scores (items 10–12).
- Starting non-invasive mask ventilation (NIV).
- Meeting 'protocolised' criteria for NIV: SVC (supine) $\leq 50\%$ predicted.
- Invasive mechanical ventilation by intubation.
- Invasive mechanical ventilation by tracheostomy.
- Death.

Time to respiratory event is reached whenever any of the criteria has first been met.

The following time-to-event secondary efficacy variables will be evaluated using Cox's proportional hazards regression:

1. Time to tracheostomy, continuous ventilator dependence, or death (TRCVDDTH)
2. Time to NIV or death (NIVDEATH)
3. Time to respiratory event (RESPEVNT)

Individual components of all the composite endpoints will be analysed in the same fashion:

1. Time to continuous ventilator dependence (ALSFRS-R item 12 ≤ 1 ; CVD)
2. Time to decline from baseline in any ALSFRS-R respiratory domain score (FRSBR1D)
3. Time to SVC (supine) $\leq 50\%$ of predicted (SVC50PP)
4. Time to non-invasive mask ventilation (NIV)
5. Time to intubation (INTUB)
6. Time to tracheostomy (TRACH)
7. Time to death (DEATH)

As will these additional endpoints derived from the SVC and ALSFRS-R values:

1. Time to decline from baseline SVC (supine) by $\geq 20\%$ (SVC20PD)
2. Time to decline from baseline ALSFRS-R total score by $\geq 20\%$ (FRS20PD)
3. Time to continuous use of NIV during the night (ALSFRS-R item 12 ≤ 2)

The data for the time-to-event variables will be stored in the ADTTE dataset with parameter names corresponding to those in parentheses above.

The analysis model will include an effect for treatment, and will be adjusted for randomization strata. Premature discontinuations will be treated as right-censored in the analyses. Censoring rules for different scenarios are described in **Error! Reference source not found..** For the purpose of determining the end date, survival and ventilation status are considered to be assessed daily; ALSFRS-R and SVC measurements are assessed only on study visits. For composite

endpoints, the date of last assessment is defined to be the latest date at which the endpoint can be fully assessed: that is, the earliest date in the set of latest assessments of each of its component endpoints.

Table 2. Censoring rules for time-to-event analyses.

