Scenario	Censored	End date
Event criteria fulfilled	No	Date of endpoint assessment
Event criteria fulfilled at baseline	Yes	Date of randomization
Event criteria never assessed	Yes	Date of randomization
Completed Week 48 without event	Yes	Date of last endpoint assessment
Discontinued study	Yes	Date of last endpoint assessment
Discontinued study treatment (1 day after*)	Yes	Date of last endpoint assessment
Died, when death not part of event criteria	Yes	Date of last endpoint assessment
Died, when death is part of event criteria	No	Date of death

*) to account for potential events following immediately after the study treatment discontinuation.

SAS code in the following fashion will be used to fit the statistical models:

```
proc phreg data = ADTTE;
  where ITTFL = "Y" and PARAMCD = "RESPEVNT";
  class TRTP(ref = "PLACEBO") STRATAR;
  model AVAL * CNSR(1) = TRTP STRATAR / ties = efron rl;
run;
```

For descriptive purposes, Kaplan-Meier survival curves will be plotted in addition to the statistical analysis results from the Cox models. Also, restricted mean survival time (RMST) will be described graphically at 14-day intervals from start of follow-up up to 48 weeks. These analyses are used to visually inspect the plausibility of the proportional hazards assumption.

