7.11 Changes from the clinical study protocol

Specification of the statistical model used in the primary efficacy analysis has been clarified.

All references to "treatment arm" have been changed to "treatment group" instead, to be consistent with the terminology used in the study's title.

Statistical hypotheses have been reworded to match model parameters. The core of the content remains unchanged.

Changed wording in the "data sets to be analysed" section to refer to "important protocol deviations" rather than "relevant major protocol deviations" when talking about the per-protocol

population. This change was made to be consistent with terminology across study communication. The core meaning remains unchanged.

Per-protocol analyses will be conducted in two separate PP populations, depending on the endpoint: PP up to week 12, and PP up to week 48. As key endpoints are assessed at different time points during the study, this provides better control for excluding subjects with deviations that could have affected the efficacy analyses.

Expanded interim analysis section to cover recommendation process in more detail.

Unacceptable quality SVC measurements will be excluded from the primary analysis.

Additional endpoints:

1. Time to any assistive device
2. Time to any respiratory assistive device
3. Time to continuous use of NIV during the night
4. Time to continuous use of NIV during the day and night
5. Time to tracheostomy, continuous ventilator dependence, or death

Additional analyses:

1. King's clinical stage will be estimated from the ALSFRS-R.
2. Restricted mean survival time will be described for time-to-event endpoints.
3. Dose change profiles will be described.
4. Correlations for biomarkers will be described, in a separate report.
5. Concentration-effect plots will be shown for SVC and QTc vs. OR-1896.
6. Adverse events will be reported by timing with respect to starting treatment, OR-1896 concentration at the Week 4 visit, and dose change profile.
7. Incidence rates will be reported for AEs.
8. Groups of TEAEs of special interest will be reported.
9. Confidence intervals for incidence proportions, incidence rates, risk ratios and incidence rate ratios will be reported for AESIs.
10. Narrative descriptions will be written for deaths, TESAEs and other significant TEAEs.
11. AEs will be reported in safety subgroups.
12. Many new categorical analyses for laboratory results will be included.

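### Kaplan-Meier curves and RMST for the time-to-event endpoints that exclude death treat death as censoring, so they describe a setting in which nobody dies first; the effect is modest and confined to supportive displays.

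*SAP*

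**What the plan says.** SAP 7.5.2.3 defines three composites that include death: respiratory event; NIV or death; and tracheostomy, continuous ventilator dependence or death. It then adds single endpoints: "Individual components of all the composite endpoints will be analysed in the same fashion". Of the seven listed, six exclude death: CVD, FRSBR1D, SVC50PP, NIV, INTUB and TRACH. A further group follows ("As will these additional endpoints derived from the SVC and ALSFRS-R values"): SVC20PD, FRS20PD and continuous night-time NIV, none of which counts death. SAP 7.5.3.1 sends the two assistive-device endpoints down the same route, which makes eleven.

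For the scenario "Died, when death not part of event criteria", Table 2 censors the subject at the date of the last endpoint assessment.

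Two displays accompany the Cox models: "For descriptive purposes, Kaplan-Meier survival curves will be plotted in addition to the statistical analysis results from the Cox models", and "restricted mean survival time (RMST) will be described graphically at 14-day intervals from start of follow-up up to 48 weeks". SAP 7.11 sets no limit on the second: "Restricted mean survival time will be described for time-to-event endpoints". A second purpose follows in 7.5.2.3: "These analyses are used to visually inspect the plausibility of the proportional hazards assumption". Neither document plans a cumulative incidence function or any other competing-risk summary.

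**The concern.** A subject who has died can no longer start NIV or reach an SVC threshold. Death before the event is therefore a competing event and not loss to follow-up. Censoring it is acceptable for a Cox model, which then estimates a cause-specific hazard ratio. It is not neutral for a curve read as absolute risk. 1-KM then estimates what the risk would be if death were removed, and the area under the KM curve counts event-free weeks that dead subjects did not live.

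Death is not rare in this disease. From the dexpramipexole phase III study the SAP says that "a 15% mortality rate at 12 months can be assumed" for placebo. What is at stake is how the study report describes, in absolute terms, how many subjects reached NIV, an SVC threshold or a functional decline, and when.

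**Working it through.** The documents give no event rates for these endpoints, so there is no plan figure to reproduce. The check sizes the gap over a stated range.

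**Inputs**
- Placebo mortality of 15% at 12 months (protocol 8.2, SAP 5). This is an upper bound for death before the event; 3% and 5% are assumed as lower values.
- Levosimendan mortality of 12%, reading the plan's 20% relative improvement in survival as 0.15 × 0.8 (assumption).
- Component event rates by week 48, expressed as 1-KM, of 10% to 60% (assumption).
- Group sizes of 150 placebo and 300 levosimendan (protocol 8.2, SAP 5).
- Constant, independent hazards over 48 weeks (assumption).

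**Formulas.** Let p be 1-KM with death censored and d the 48-week risk of death when the component event is set aside. Then Le = -ln(1-p), Ld = -ln(1-d) and t = Le + Ld.
- Actual cumulative incidence: CIF = (Le/t) × (1 - exp(-t))
- KM RMST: 48 × (1 - exp(-Le))/Le
- Mean time alive and event-free: 48 × (1 - exp(-t))/t

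**Worked case, p = 30%, d = 15%.** Le = 0.3567, Ld = 0.1625, t = 0.5192, and 1 - exp(-t) = 1 - 0.70 × 0.85 = 0.405. CIF = 0.6870 × 0.405 = 27.8%, so 1-KM is 2.2 points too high.

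**Range: CIF in %, with the overstatement by 1-KM in points in brackets**

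| 1-KM | d = 3% | d = 5% | d = 15% |
|---|---|---|---|
| 10% | 9.85 (0.15) | 9.75 (0.25) | 9.24 (0.76) |
| 30% | 29.57 (0.43) | 29.29 (0.71) | 27.82 (2.18) |
| 50% | 49.33 (0.67) | 48.88 (1.12) | 46.58 (3.42) |
| 60% | 59.23 (0.77) | 58.71 (1.29) | 56.06 (3.94) |

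Scaling the 12-month figure to 48 weeks (15% × 48/52 = 13.8%) changes the last column only slightly: 2.0, 3.2 and 3.6 points at 30%, 50% and 60%.

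**RMST at p = 30%.** KM RMST is 48 × 0.30/0.3567 = 40.4 weeks. Time alive and event-free is 48 × 0.405/0.5192 = 37.4 weeks at d = 15% (gap about 2.9 weeks), 39.4 at 5% and 39.8 at 3%. At d = 15%, the 48 - 37.44 = 10.56 weeks lost divide in proportion to the hazards: 0.687 × 10.56 = 7.25 weeks to the event and 3.31 to earlier death. The KM version attributes 48 - 40.37 = 7.63 weeks to the event and shows none lost to death.

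**Between groups.** Give both groups the same component hazard, with mortality of 15% and 12%. The KM curves coincide. The cumulative incidences differ by 0.15, 0.45, 0.70 and 0.81 points at 1-KM of 10%, 30%, 50% and 60%, and are higher on levosimendan because more subjects live long enough to have the event. A simple binomial standard error of the difference, ignoring other censoring, is sqrt(p(1-p)(1/150 + 1/300)) = sqrt(0.01 p(1-p)), or 3.0, 4.6, 5.0 and 4.9 points. The shift is thus 0.05, 0.10, 0.14 and 0.17 of a standard error.

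**The case against.** The other side has a good case, and most of it stands as a limit on the weight of the point.

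- **No test is affected.** SAP 7.5.2 makes endpoints outside the hierarchy supportive. The time to respiratory event counts death, and CAFS ranks it. A reader might infer that the Cox results for the components are invalid. They are not: they remain cause-specific hazard ratios.
- **The displays also serve a diagnostic purpose.** For a cause-specific Cox model, KM with death censored is a suitable proportional-hazards check. But the SAP states a descriptive purpose first, and it is that use which misleads.
- **15% is an upper bound.** It is all-cause 12-month mortality from another trial. SAP 6.2.5 and Table 2 end time-to-event follow-up one day after study treatment stops, and deaths after the component event do not compete. Only deaths on treatment and before the event matter.
- **Other information exists.** Efficacy data are tabulated by visit (SAP 7.5) and survival has its own KM curves (SAP 7.9.1), so these are not the only absolute descriptions. NIV, tracheostomy and ventilator dependence each have a specific composite with death. SVC50PP, FRSBR1D and intubation meet death only in the broad respiratory-event composite. The two 20% decline endpoints are in no time-to-event composite with death. A separate survival curve cannot be combined with a component curve by eye to recover incidence.

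A reader might also infer that the curves would show a spurious component benefit for levosimendan if it lowers mortality. The calculation does not support that. With equal component hazards the KM curves coincide, and it is the cumulative incidences that separate slightly, in the other direction. That is a difference in estimand and not a false benefit.

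**Conclusion.** The point holds as a limited one. For the eleven endpoints that exclude death, the planned KM curves and RMST describe a setting without death. The direction is certain: 1-KM cannot be below the actual cumulative incidence, and RMST cannot be below mean time alive and event-free. The size is modest. In the likelier range, where few subjects die on treatment before the event, the overstatement is at most about 1.3 points; the 2 to 4 points need the whole assumed 15% to compete. The between-group effect is below 1 point and under 0.2 of a standard error. These sizes rest on constant independent hazards, assumed event rates and assumed death-first risks, none of which the documents supply for these endpoints. The point is a correction to how supportive results are described and does not threaten any conclusion the trial is designed to draw.

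**What to change.** Add a sentence to SAP 7.5.2.3, applied also to 7.5.3.1. For endpoints that exclude death, the descriptive displays will code death before the event as a competing event at the date of death, in place of censoring at the last endpoint assessment. Aalen-Johansen cumulative incidence will be plotted by treatment group, and restricted mean time lost will be reported as the area under the same curve. The sentence should also say whether deaths after treatment discontinuation, which the current rule leaves censored, stay so.

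Keep the cause-specific Cox models unchanged. Keep KM and RMST for the composites that include death and for the death endpoint itself. For the other endpoints keep them for the proportional-hazards check, labelled as censoring death.

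The cost is small: one SAP sentence, a recoded event indicator and an option in the plotting code (PROC LIFETEST with EVENTCODE=). It needs no new data and changes no test. The downside is an additional set of descriptive plots. If those are not wanted, the label alone would prevent the misreading.

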7.5.2.4 Clinical Global Impression

Clinical Global Impression (CGI) is used to rate the severity of subjects' clinical condition. The subjects themselves assess their clinical condition with a visual analogue scale (VAS). A score of 0 indicates (in the 100 millimetre scale) that the subject is completely well without any disability; and a score of 100 indicates the worst possible severity of the condition. This rating is based on symptoms and function during the past 1 week, and the score should reflect the average clinical condition during the week.

CGI through Week 48 will be evaluated using the MMRM and estimates for the treatment effect at each study visit will be obtained using contrasts. Statistical significance of the treatment difference at Week 48 will be tested. Descriptive statistics will be reported by treatment group for each study visit.

7.5.2.5 Borg Category Ratio 10 Scale

The Borg Category Ratio 10 (CR10) scale will be used in the assessment of dyspnoea (Borg GA, 1982). The subjects will be asked to point out a score quantifying their perception on the intensity of dyspnoea on the CR10 scale at rest in sitting and supine positions (immediately before SVC measurements). Orthostatic changes between sitting and supine positions will be calculated.

Borg CR10 in the supine position will be evaluated through Week 12 using the MMRM. Estimates for the treatment effect at Week 12 will be derived from model-based contrasts, along with a test result for its statistical significance. Additionally, sitting, supine and orthostatic changes will be evaluated in a similar fashion through Week 48, with estimates for the treatment effect obtained at each study visit. Descriptive statistics for all Borg CR10 variables will be reported by treatment group for each study visit.

7.5.2.6 Epworth Sleepiness Scale

Daytime somnolence will be assessed by the Epworth Sleepiness Scale (ESS) (Johns MW, 1991). The ESS is a self-administered questionnaire with 8 questions. Subjects are asked to rate, on a 4-point scale (0-3), their usual chances of dozing off or falling asleep while engaged in eight different activities. Score 0 indicates 'no chance of dozing' and 3 indicates 'high chance of dozing'. Most people engage in those activities at least occasionally, although not necessarily every day. If one has not engaged recently in a certain activity, the subject will estimate how sleepy he/she would have been during that activity. The ESS score (the sum of 8 item scores, 0-3) can range from 0 to 24. The higher the ESS score, the more pronounced the subject's average daytime sleepiness. A sum score of 10 or more suggests medical attention may be required.

The ESS through Week 48 will be evaluated using the MMRM and estimates for the treatment effect at each study visit will be obtained using contrasts. Further, results of a categorical analysis of the ESS dichotomised at the clinically significant threshold of 10 will be reported. For this purpose, a repeated measures binary logistic regression model will be fitted using the generalised estimating equation approach. Descriptive statistics of both the original measurements as well as the dichotomised values will be reported by treatment group for each study visit.

7.5.2.7 Pittsburgh Sleep Quality Index

The Pittsburgh Sleep Quality Index (PSQI) is a self-rated questionnaire assessing sleep quality and disturbances over a preceding 1 month period (Buysse DJ et al., 1989). The questionnaire consists of 19 self-rated questions/items which are included in the scoring. These 19 items are combined to form seven component scores (subjective sleep quality, sleep latency, sleep duration, habitual sleep efficiency, sleep disturbances, use of sleeping medication, daytime dysfunction) each of which has a range of 0-3 points. In all components, a score of 0 indicates no difficulty, while a score of 3 indicates severe difficulty. The seven component scores are then added to yield one global score, with a range of 0-21 points, 0 indicating no difficulty and 21

indicating severe difficulties in all items. The derived variable will be the PSQI global score. A global score of 5 or more indicates poor sleep quality.

During the study, we have observed subjects systematically reporting bedtimes at implausible hours of the day. Specifically, it seems likely that a significant number of subjects have reported their bedtimes using a 12-hour clock rather than the expected 24-hour clock. To correct for this, we will use the following procedure: If the reported bedtime falls within 6 AM and 3 PM, and applying a correction of 12 hours would bring the calculated sleep duration within a 2-hour tolerance of the reported sleep duration, the corrected bedtime will be used instead of the originally reported one.

The PSQI will be analysed using the same methods described for the ESS in section [7.5.2.6 above](#), with the modification of using the PSQI's own clinically significant threshold of 5.

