6.2.7 Pittsburgh Sleep Quality Index

PSQI is a self-rated questionnaire which assesses sleep quality and disturbances over a preceding 1 month period (Buysse DJ et al., 1989). There are a total of 19 self-rated questions/items which are included in the scoring. These 19 items are combined to form seven component scores (subjective sleep quality, sleep latency, sleep duration, habitual sleep efficiency, sleep disturbances, use of sleeping medication, daytime dysfunction) each of which has a range of 0-3 points. In all components, a score of 0 indicates no difficulty, while a score of 3 indicates severe difficulty. The seven component scores are then added to yield one global score, with a range of 0-21 points, 0 indicating no difficulty and 21 indicating severe difficulties in all items. The derived variable will be the PSQI global score. Global score of >5 indicates poor sleep quality.

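### The PSQI bedtime correction in SAP 7.5.2.7 depends on time awake in bed, so the same 12-hour-clock error is repaired up to about 2 h awake and kept beyond that

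*SAP*

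**What the plan says.** SAP 7.5.2.7 reports implausible bedtimes seen during the study and thinks it likely that "a significant number of subjects have reported their bedtimes using a 12-hour clock rather than the expected 24-hour clock". The repair has two conditions, both required:

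- a window: "If the reported bedtime falls within 6 AM and 3 PM";
- an agreement test: "applying a correction of 12 hours would bring the calculated sleep duration within a 2-hour tolerance of the reported sleep duration".

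When both hold, "the corrected bedtime will be used instead of the originally reported one". The SAP does not define the calculated duration. It states no handling for a bedtime that is inside the window but fails the agreement test, so the reported value is analysed.

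The PSQI components include "habitual sleep efficiency, sleep disturbances, use of sleeping medication, daytime dysfunction", "each of which has a range of 0-3 points", and sum to a global score of 0-21. Protocol 6.2.7 lists the same components. For the categorical analysis the SAP states: "A global score of 5 or more indicates poor sleep quality".

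PSQI is named in the secondary objective (Protocol 2.2, SAP 3.2). It is not among the five endpoints of the testing hierarchy, and SAP 7.5.2 treats everything outside that hierarchy as supportive. Among the sensitivity analyses in SAP 7.5.4, the only one that names PSQI concerns paper versus electronic collection (7.5.4.10). The outlier provision in SAP 6.2.6 is general and optional.

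**The concern.** A shift of bedtime changes only one duration: the interval from going to bed to getting up, with or without latency removed. The gap between that interval and reported sleep is time spent awake in bed, and this determines sleep efficiency. The decision to repair an entry therefore depends on a quantity that the instrument is scoring.

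Two subjects can make the identical clock error. The one who lies awake for up to about 2 hours is repaired. The one who lies awake longer keeps an impossible time in bed and gets the worst efficiency score. One subject near the 2-hour line can be repaired at one visit and not at the next, which produces a change that did not occur. At stake are the PSQI MMRM and the dichotomised poor-sleep analysis.

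**Working it through.** The plan gives no figure to reproduce, so the check applies the rule to defined cases.

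**Inputs.** The window and the 2-hour tolerance come from SAP 7.5.2.7. The efficiency bands are an assumption, not in the documents: at least 85% scores 0, 75-84% scores 1, 65-74% scores 2, below 65% scores 3. The bands only size the error; the selectivity does not depend on them.

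**Formulas.** Let T be true time in bed, A hours awake in bed, and S = T - A reported sleep. Every case carries the 12-hour error.

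- Gap after the shift = T - S = A, so the entry is repaired if and only if A ≤ 2.
- If repaired, efficiency = S/T. If not, efficiency = S/(T + 12).

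**Efficiency at the cut**, (T - 2)/T: 71% for T = 7 h, 75% for 8 h, 78% for 9 h, 80% for 10 h, 83% for 12 h.

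**Cases.** For T = 9 h: in bed at 22:00, entered as 10:00, up at 07:00.

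| T (h) | S (h) | A (h) | Repaired | True efficiency | Efficiency used | Component true → used |
|---|---|---|---|---|---|---|
| 9 | 7.5 | 1.5 | yes | 83% | 83% | 1 → 1 |
| 9 | 6.5 | 2.5 | no | 6.5/9 = 72% | 6.5/21 = 31% | 2 → 3 |
| 9 | 5 | 4 | no | 5/9 = 56% | 5/21 = 24% | 3 → 3 |
| 10 | 8 | 2 | yes | 80% | 80% | 1 → 1 |
| 10 | 7.5 | 2.5 | no | 7.5/10 = 75% | 7.5/22 = 34% | 1 → 3 |

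The last two rows, taken as two visits of one subject with the clock error at both, show a false 2-point worsening: the true component is 1 each time.

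**Size of the error (T from 7 to 12 h).** Unrepaired entries always score 3, because the efficiency used never exceeds 9.75/24 = 41%.

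- An excess exists only while true efficiency is at least 65%, that is 2 < A ≤ 0.35T: up to 2.8 h awake for T = 8 and 3.15 h for T = 9.
- A 2-point excess needs 2 < A ≤ 0.25T, hence T above 8 h.
- A 3-point excess would need 2 < A ≤ 0.15T, hence T above 13.3 h, outside this range.

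Crossing the cut-off of 5 needs a true global score of 4 with a 1-point excess, or 3 or 4 with a 2-point excess.

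**Limit of this range.** Above 12 h in bed the unshifted interval wraps round. A true 20:00-09:00 (13 h) entered as 08:00 gives 1 h in bed, so an unrepaired entry there would err in the other direction.

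**Other reading of the duration.** If latency L is subtracted first, the cut moves to A = 2 + L. At T = 9 the efficiency at the cut becomes (9 - 2.5)/9 = 72% for L = 0.5 h and (9 - 3)/9 = 67% for L = 1 h. With L = 0.75 h the 6.5-hour sleeper is repaired, since 9 - 0.75 - 6.5 = 1.75. The line moves, but repair still depends on wakefulness.

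**Illustration among erroneous entries only** (assumed T about 9 h with SD 1 h, gamma-distributed A). Mean awake times of 1, 2 and 3 h give 91%, 59% and 39% repaired. The mean component is 0.44, 1.43 and 2.01 against true values of 0.34, 1.14 and 1.72.

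**The case against.** The tolerance has a legitimate purpose: it asks for corroboration before a patient's own answer is overwritten, and it protects people who really sleep by day. The rule contains no treatment term and applies identically in both groups. It touches one of seven components of a supportive score, the range of wakefulness with a scoring error is narrow, and the least efficient sleepers have no error at all because they already score 3.

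The points on materiality stand. The protective argument does not need the 2-hour test: someone in bed from 08:00 to 16:00 has 8 h as entered and 20 h after a shift, so a limit on time in bed alone leaves that entry unchanged.

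A reader might infer that errors are repaired for good sleepers and left in for poor ones. The documents do not support that. The dividing line is about 2 h awake in bed, not the global score; the repaired subject at 83% efficiency already scores 1 on the component, and subjects who sleep badly on other components can be repaired too. A reader might also infer a biased treatment effect. That would require the groups to differ in wakefulness among erroneous entries, and nothing in the documents shows this.

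**Conclusion.** The point holds as a minor defect in a stated derivation rule. On either reading of the calculated duration, repair of the clock error depends on wakefulness in bed. For true times in bed of 7 to 12 h, and with time in bed as the duration, unrepaired entries carry 19 to 24 h in bed. Under the assumed bands the excess is 0 to 2 points out of 21, always towards worse sleep in that range.

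No listed sensitivity analysis would show the effect. Its importance is limited: PSQI is supportive, the SAP does not say how many records are affected, and no size or direction for the treatment difference can be derived. The selectivity follows from the SAP wording; the point sizes rest on the assumed bands.

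**What to change.** In SAP 7.5.2.7:

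1. Define the calculated sleep duration, including whether latency is subtracted.
2. For reported bedtimes from 06:00 to 15:00, keep the shift where the present 2-hour test is met. Also shift when the unshifted time in bed is implausibly long (for example over 14 h, a stated judgement) and the shifted one is plausible (for example at most 14 h), without requiring agreement with reported sleep.
3. Set the bedtime to missing when time in bed is implausible both ways. The two intervals always differ by 12 h, so this clause needs a lower limit as well (for example 3 h, also a judgement): an unshifted 14.5 h becomes 2.5 h. The same lower limit can identify the wrapped entries above 12 h.
4. Report PSQI without the correction as a sensitivity analysis.

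Checks: 10:00 to 07:00 with 6.5 h sleep is 21 h unshifted and 9 h shifted, so it is now repaired. 08:00 to 16:00 stays unchanged.

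The 2-hour test should not be replaced by a requirement that shifted time in bed be no shorter than reported sleep. An entry of 10:00 to 06:00 with 8.5 h reported sleep is repaired today (gap 0.5 h), but would fail because 8 < 8.5 and would be scored at 8.5/20 = 42.5%.

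The cost is SAP wording, a short change to the derivation code and one extra table. A few entries may be misassigned at the chosen limits. A bedtime set to missing also loses that visit's global score, because SAP 6.2.5 treats a summary score as missing when any item is missing and does not list PSQI for imputation.
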